### 5.3. Risk/Benefits

Cysteamine is an aminothiol that drives a disulfide exchange reaction converting cystine into cysteine and cysteine-cysteamine mixed disulfide.

PROCYSB is approved for the management of nephropathic cystinosis in children and adults. PROCYSB is contraindicated in patients who have developed hypersensitivity to it or to cysteamine or penicillamine (PROCYSB Package Insert). Most commonly reported adverse reactions ( $\geq 5\%$ ) are vomiting, abdominal pain/discomfort, headaches, nausea, diarrhea, anorexia/decreased appetite, breath odor, fatigue, dizziness, skin odor, and rash (PROCYSB Package Insert). Less common adverse events associated with cysteamine include: CNS symptoms such as seizures, dizziness, lethargy, somnolence, depression, and encephalopathy; gastrointestinal tract symptoms including nausea, vomiting, anorexia and abdominal pain, sometimes severe. In addition, gastrointestinal ulceration and bleeding have been reported in patients on cysteamine therapy. Cysteamine has occasionally been associated with reversible leucopenia, abnormal liver function studies, skin lesions, headache, tinnitus, diplopia, blurry vision, loss of vision, pain behind the eye or pain with eye movement (PROCYSB Package Insert).

RP103, Cysteamine Bitartrate Delayed-release Capsules, was designed to be a delayed-release product of cysteamine bitartrate which would avoid some of the unwanted side

effects of the compound and extend the duration of effective treatment in a Q12H dosing regimen, thereby helping to improve compliance over the current Q6H round the clock dosing required for immediate release formulation Cystagon effectiveness. Clinical studies have demonstrated that patients with cystinosis are able to maintain a plasma WBC cystine level in the target range equal to or below 1.0 nmol  $\frac{1}{2}$ cystine/mg protein using a Q12H delayed-release formulation (EC-cysteamine or RP103).

A review of the literature, post-marketing experience of Cystagon since 1994 by the FDA and 1997 by the EMA, the UCSD experience with EC-cysteamine, and Raptor's studies in healthy volunteers, cystinosis patients, [REDACTED] and H [REDACTED] with RP103, does not reveal any additional risks to human subjects than what is described in the PROCYSBI Package Insert.

#### 5.4. Study Rationale

On April 30, 2013 PROCYSBI (the marketed name for RP103) was approved by FDA in the US for the management of nephropathic cystinosis in adults and children 6 years and older (NDA 203-389). Raptor is developing this delayed-release formulation with extended-release properties of cysteamine bitartrate (RP103).  
[REDACTED]

A recent study in a cohort of children with biochemically and/or genetically confirmed mitochondrial diseases found that their plasma thiols and their redox state are altered, indicating an increase in oxidative stress and depletion of antioxidant supplies. The ability of cysteamine to increase cellular thiol pool can potentially address the relative thiol deficiency in those patients and likely to address the underlying pathophysiology of the diseases. In addition, oxidative stress has been implicated in the pathogenesis of complications of mitochondrial diseases, the ability of cysteamine to directly scavenge reactive oxygen species (ROS) will likely further counterbalance the increased oxidative stress and improve the compromised mitochondria functions and lead to potential treatment effect. Moreover, in a recent publication about a new compound, EPI-743, that seems to have some efficacy in Leigh syndrome, the authors concluded that data support glutathione as a “redox blood signature” in mitochondrial disorders and its use as a clinical trial endpoint in the development of mitochondrial disease therapies.

Cysteamine is an aminothiol that participates in a thiol-disulfide interchange reaction converting cystine into cysteine and cysteine-cysteamine mixed disulfide. This cysteine-cysteamine mixed disulfide can exit the lysosome through the lysosome membrane, as it is transported through the intestinal barrier or the blood brain barrier, by the lysine transporter or a lysine-like transporter, the PQLC2 protein. This mechanism is the rationale that has been successfully used to treat patients with cystinosis for more than 20 years. This biochemical reaction results in an increase of the cellular thiol pool, making more cysteine available for glutathione (GSH) synthesis. Glutathione is composed of the amino acids cysteine, glutamate and glycine. The availability of cysteine, which exists primarily as cystine, is the major rate-limiting factor in GSH production. Recent findings by Mancuso *et al.* reinforce the notions that in mitochondrial diseases oxidative stress is important and can be reduced by administration of a cysteine donor.

Moreover, cysteamine is almost exclusively metabolized in hypotaurine then taurine, and taurine deficiency appears to diminish the formation of 5-taurinomethyluridine and causes inefficient decoding for the mitochondrial codons of leucine, lysine, glutamate and glutamine. The resulting reduction in the biosynthesis of mitochondria-encoded proteins deprives the respiratory chain of subunits required for the assembly of respiratory chain complexes. Hence, taurine deficiency is associated with a reduction in oxygen consumption, an elevation in glycolysis and lactate production and a decline in ATP production. A similar sequence of events takes place in mitochondrial diseases MELAS (mitochondrial myopathy, encephalopathy, lactic acidosis and stroke-like episodes) and MERRF (myoclonic epilepsy and ragged-red fiber syndrome). In both diseases, mutations in their respective tRNAs interfere with the formation of 5-taurinomethyluridine in the wobble position. Hence, the taurine-deficient phenotype resembles the phenotypes of MELAS and MERRF.

### **5.5. Dose Rationale**

RP103 will be administered at the same doses and following a progressive dose titration as used in patients with cystinosis for ~ 20 years, since this has been associated with better tolerability.

### **5.6. Study Conduct**

This study will be conducted in compliance with the protocol approved by the local Institutional Review Boards (IRB) or Ethics Committees (EC), and according to FDA and ICH Good Clinical Practice guidelines.

### **5.7. Study Population**

Subjects who have completed all visits associated with Study RP103-MITO-001 and meet the inclusion and exclusion criteria for RP103-MITO-002 (specified in Section 8.1 and 8.2) will be offered enrollment in this extension study.

Patients with inherited mitochondrial diseases associated with nuclear or mitochondrial DNA mutations that impair the respiratory chain. These include, but are not limited to the following clinical syndromes: Leber's hereditary optic neuropathy; myoclonic epilepsy and ragged-red fibers (MERFF); mitochondrial encephalomyopathy, lactic acidosis, and stroke-like syndrome (MELAS); Kearns-Sayre syndrome; subacute necrotizing encephalopathy (Leigh Syndrome); POLG-related disorders (Alpers-Huttenlocher Syndrome, Autosomal Dominant Progressive External Ophthalmoplegia, Autosomal Recessive Progressive External Ophthalmoplegia, Childhood Myocerebrohepatopathy Spectrum Disorders, Myoclonic Epilepsy Myopathy Sensory Ataxia, POLG-Related Ataxia Neuropathy Spectrum Disorders); Mitochondrial neurogastrointestinal encephalopathy syndrome (MNGIE), also called myoneurogastrointestinal encephalopathy syndrome or POLIP syndrome; others, e.g., mitochondrial cardiomyopathies and other syndromes due to multiple mitochondrial DNA deletions.

Up to 25 subjects will be enrolled (the maximum number of participants planned for Study RP103-MITO-001).

## 6. STUDY OBJECTIVES AND ENDPOINTS

The objective of this study is to assess safety, tolerability and efficacy of RP103 in patients with inherited mitochondrial disease.

### 6.1. Primary Objective

To assess safety, tolerability and efficacy of long-term repeat dosing of RP103 in children with inherited mitochondrial disease.

### 6.2. Secondary Objective

To assess the steady-state pharmacokinetics (PK) and pharmacodynamics (PD) of RP103 at steady state, in children with inherited mitochondrial disease.

### 6.3. Study Endpoints

#### 6.3.1. Primary Endpoints

The primary outcome measure will be quality of life based upon the Newcastle Paediatric Mitochondrial Disease Scale (NPMDS)

#### 6.3.2. Secondary Endpoints

- The two preeminent symptoms previously identified during the RP103-MITO-001 study will continue to be assessed in this extension study:

Symptom	Measurement Tool(s)
Myopathy	6-minute walk (6MWT); Jama dynamometer
Dystonia	Barry-Albright Dystonia Scale
Ataxia	Friedreich Ataxia Rating Scale (FARS)
Retarded motor development	Gross Motor Function Measure (GMFM)
Reduced activities of daily living	Modified Lansky Play Performance Scale
Vision	Vision/Eye Examination (LHON subjects)

- Pharmacodynamic Biomarkers: glutathione, glutathione disulfide and lactate

## 7. OVERALL STUDY DESIGN AND PLAN

### 7.1. Study Design

This is an open-label extension study of RP103-MITO-001 to assess the safety, tolerability and efficacy of Cysteamine Bitartrate Delayed-release Capsules (RP103) for treatment of children with inherited mitochondrial disease.

Subjects who have completed all visits associated with Study RP103-MITO-001 will be offered enrollment in this extension study. If enrolled in RP103-MITO-002, subjects will return to the clinic quarterly (every 3 months) for detailed assessments.

### 7.2. Study Visits

Study visits will occur as follows:

**Day 1 (Baseline):** is the day of enrollment, and will occur simultaneously with the RP103-MITO-001 Study Exit Visit.

**Quarterly Visits:** will begin within 3 months ( $\pm 7$  days) of the RP103-MITO-002 Day 1 Visit and will continue quarterly (every 3 months).

- **Study Exit Visit:** will take place upon study completion (i.e. marketing approval has been granted for RP103 and the subject is able to obtain in commercially), study termination, or upon individual subject termination

### **7.3. Study Drug Dosing Methodology**

Upon RP103-MITO-002 study entry, subjects will continue on the last total daily dose of RP103 taken during the previous RP103-MITO-001 study. Subsequent RP103 dose adjustments are permitted (e.g. as the subject grows, or if deemed necessary by the Investigator for tolerability reasons).

The Sponsor's medical officer may be consulted for assistance making RP103 dose adjustment decisions at any time during the study. NOTE: For each subject, when calculating the number of capsules to be taken every 12 hours (i.e. half of the prescribed total daily dose), if rounding is required to get a whole number of capsules to be taken, then rounding should be down and not up.

### **7.4. Randomization**

Subjects will not be randomized.

### **7.5. Duration**

Study duration is up to 24 months.

## **8. SELECTION OF SUBJECTS**

Subjects must continue to meet the following eligibility criteria that had been specified in the previous Study RP103-MITO-001:

### **8.1. Inclusion Criteria**

1. Completed all study visits associated with Study RP103-MITO-001.
2. Body weight  $\geq 5$  kgs.
3. The subject must be willing to abstain from initiating dietary supplements and non-prescribed medications except as allowed by the Investigator, throughout the study (from Day 1 to Study Exit).

4. Willing and able to comply with study drug dosing requirements, i.e. ingest the RP103 capsules intact, or sprinkled in liquid or soft food, or using a G-tube.
5. Sexually active female subjects of childbearing potential (i.e., not surgically sterile [tubal ligation, hysterectomy, or bilateral oophorectomy]) must agree to utilize two of the following acceptable forms of contraception throughout the study (from Day 1 to Study Exit):
  - a) Hormonal contraception: birth control pills, injection, patch, vaginal ring or implant;
  - b) Condom or diaphragm, with spermicide;
  - c) Intrauterine device (IUD)
  - d) Sterile male partner (vasectomy performed at least 6 months prior to the study).
6. Patient's legally authorized representative must provide written informed consent; Patient must provide assent, if required by local/institutional requirements.

### **8.2. Exclusion Criteria**

1. Documented diagnosis of concurrent inborn errors of metabolism
2. Platelet count, lymphocyte count or hemoglobin below the lower limit of normal (LLN) at the Day 1 (RP103-MITO-001 Study Exit) Visit.
3. Hepatic insufficiency with liver enzyme tests (alkaline phosphatase, AST or ALT) greater than 2.5 times the upper limit of normal (ULN) at the Day 1 (RP103-MITO-001 Study Exit) Visit.
4. Bilirubin > 1.2 g/dl at the Day 1 (RP103-MITO-001 Study Exit) Visit.
5. Inability to complete the elements of the study, e.g., coma, hemodynamic instability or requiring continuous ventilator support.
6. Malabsorption requiring TPN, chronic diarrhea, bouts of pseudo obstruction.
7. Severe end-organ hypo-perfusion syndrome secondary to cardiac failure resulting in lactic acidosis.
8. Patients with suspected elevated intracranial pressure, pseudotumor cerebri (PTC) and/or papilledema.
9. Severe gastrointestinal disease including gastroparesis.
10. History of drug or alcohol abuse.
11. History of pancreatitis.
12. Participated in an investigational drug trial (except Study RP103-MITO-001) within 30 days or, within 90 days for a biologic, device, or surgical treatment, for inherited mitochondrial diseases prior to the Day 1 (RP103-MITO-001 Study Exit) Visit.
13. Known or suspected hypersensitivity to cysteamine and penicillamine.
14. Female subjects who are nursing, planning a pregnancy, known or suspected to be pregnant, or with a positive serum pregnancy test at the Baseline visit.

15. Patients who, in the opinion of the Investigator, are not able or willing to comply with the protocol.

### **8.3. Removal of Subjects from Study Participation**

Subjects will be informed that they are free to withdraw from the study at any time and for any reason. The Investigator may withdraw a subject from the study if, in the Investigator's opinion, it is not in their best interest to continue participation. Notification of early termination will immediately be made to the Sponsor's representative(s).

In case of early termination, the subject must return to the clinic for a Study Exit visit within 4 weeks after last dosing (28 days +/- 7 days) and perform all assessments detailed in the Schedule of Events (Section 2). The reason for discontinuation will be recorded in source documentation and the eCRF.

Subjects may be withdrawn from the study for the following reasons:

- Adverse event(s);
- Pregnancy;
- Withdrawal of consent;
- Subject non-compliance;
- Investigator decision;
- Sponsor decision, i.e., cancellation of drug development;
- Request from regulatory agency (e.g., FDA), Institutional Review Board, or Ethics Committee.

## **9. TREATMENT OF SUBJECTS**

### **9.1. Study Treatment**

Raptor Pharmaceuticals Inc. will provide the Investigator with adequate quantities of RP103 (see **Table 1**). The active ingredient in RP103 is cysteamine bitartrate; dosage in its formulation is expressed as mg of cysteamine free base.

**Table 1: Study Drug**

Study Drug	Cysteamine Bitartrate Delayed-release Capsules (RP103)
Form a	Capsules
Strength b	25 mg and 75 mg
Supplier	Raptor Pharmaceuticals Inc.

a Specific ingredients/purity will be identified on the Certificate of Analysis (or equivalent) that is supplied for RP103.

b Provided strength is as cysteamine free base.

#### **9.2. Identity of Investigational Product**

The 25 mg strength Cysteamine Bitartrate Delayed-release Capsules (RP103, test product) are a size 3 two-toned blue hard gelatin capsules or light blue single tone hard gelatin capsules imprinted with “Raptor/103” or “Raptor” logo and “25 mg” in white ink. They are provided in 60-count bottles.

The 75 mg strength Cysteamine Bitartrate Delayed-release Capsules (RP103, test product) are a size 0 blue two-toned hard gelatin capsules imprinted with “Raptor/103” or “Raptor” logo and “75 mg” in white ink. They are provided in 150-count bottles.

#### **9.3. Storage of Investigational Products**

Cysteamine Bitartrate Delayed-release Capsules (RP103) should be stored at controlled room temperature (maintained at 20-25°C, mean temperature not more than 25°C, with excursions permitted from 15 to 30°C), protected from light and moisture. The product must be kept in the original bottle and should not be dispensed into another container. Do not remove the oxygen absorber and desiccant.

#### **9.4. Concomitant Medications and Excluded Therapies**

All patients will be asked about concomitant medications at study entry and at each study visit. For patients entering the study on a chronic concomitant medication, adequate clarification of the reason for taking that medication must be documented in source documentation (e.g., medical history). Information about medications used after study entry must also be recorded. Patients must observe the restrictions listed here for the specified time periods and throughout the study.

At the Baseline visit, the patient or parent will be provided with a diary to record protocol specified medications and information (e.g., missed school days, seizure activity) and instructed on its completion. At each study visit, the Investigator staff will review the diary for completeness, errors/corrections and dosing compliance. Staff will issue a new diary for use until the next study visit. All diaries will be collected at study completion.

Illegal or recreational alcohol or drug use is not allowed during the study. If the Investigator suspects illegal or recreational alcohol or drug use, alcohol or drug tests may be administered at the discretion of the Investigator.

### **9.5. Study Treatment Administration and Compliance**

Upon RP103-MITO-002 study entry, subjects will continue on the last total daily dose of RP103 taken during the RP103-MITO-001 study. Study drug labeled for the previous Study RP103-MITO-001 must be taken for the morning dose and associated PK blood draws on the day of Study Exit (which is also RP103-MITO-002 Day 1). Then, study drug labeled for Study RP103-MITO-002 is to be dispensed for the evening dose (RP103-MITO-002 Day 1) and - to be taken every 12 hours for the remainder of participation in Study RP103-MITO-002.

Detailed instructions for dosing are provided in Section 15.4 and subjects will also be provided with a handout with those same instructions. RP103 administered during study visits will be under the supervision of Investigator personnel.

A daily diary of protocol-specified medications will be maintained throughout the study and will be used to assess RP103 dosing compliance.

## 10. STUDY PROCEDURES

### 10.1. Schedule of Study Procedures

Before any study-specific procedures are performed, the patient and legally authorized representative (if appropriate) must receive an explanation of all study procedures and must sign and date an Institutional Review Board (IRB) or Ethics Committee (EC)-approved written informed consent and assent (if applicable) form.

#### 10.1.1. Day 1 (Baseline) Visit Procedures

- Obtain written consent, and assent if applicable
- Review data collected at the RP103-MITO-001 Study Exit Visit and review/confirm subject meets eligibility criteria for this extension study. If so, proceed with enrollment.
- The following study procedures can be carried forward from the RP103-MITO-001 Study Exit Visit and do not need to be duplicated:
  - Measure vital signs (blood pressure, heart rate, respiratory rate, and oral body temperature).
  - Measure height, body weight and head circumference; calculate BMI and BSA.
  - Perform physical examination.
  - Obtain a 12-lead ECG.
  - Administer age-specific NPMDS (only if not administered during RP103-MITO-001 Exit visit)
  - For each subject, perform the assessments associated with their preeminent symptoms already specified during Study RP103-MITO-001 (and detailed in Section 6.3.2 Secondary Endpoints).
  - Collect blood samples for laboratory tests, within 30 minutes before/after RP103 dose
  - Collect breath samples for hydrogen sulfide testing.
  - Collect and review seizure activity since the previous clinic visit. Dispense a paper seizure diary if applicable (or print from [www.seizuretracker.com](http://www.seizuretracker.com) website).
- For females, re-assess childbearing potential and menstrual history.
- The final dose of study drug labeled for the RP103-MITO-001 should have been taken that morning. Administer study drug labeled for RP103-MITO-002, with instructions to subject to take first dose of study drug for RP103-MITO-002 12 hours later than evening. Dispense RP103 for home administration. Explain and provide the subject and/or caregivers with RP103 Dosing Instructions.
- Provide subject and/or caregivers with re-training on the medications diary; dispense a blank diary for subjects to complete until the next study visit.
- Schedule or confirm the next study visit.

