### Schedule of Events Footnotes

- a RP103-MITO-001 Study Exit is to take place on the same day as RP103-MITO-002 Day 1 (Baseline). Data collected from the RP103-MITO-001 study (i.e. medical history, ongoing adverse events, concomitant medications, Study Exit vital signs) may be carried forward to the extension study clinical database. Data recording and entry instructions will be supplied via the electronic CRF instructions.
- b Clinical Laboratory Tests and PD Biomarkers are specified in Protocol Table 2; Samples for Clinical Laboratory Tests and PD Biomarkers should be collected at the same time as PK blood samples.
- c PK blood samples will be collected within 30 minutes before or after the RP103 morning dose.
- d Seizure activity may be recorded by patients/caregivers using a paper seizure diary handed out by the site, or the form provided on [www.seizuretracker.com](http://www.seizuretracker.com) website. If patients use the web-based form, it must be printed out and used as source documentation for any associated CRF data entry.
- e RP103 from the previous Study RP103-MITO-001 must be taken for the morning dose and associated PK blood draws on the day of Study Exit. Then, RP103 for Study RP103-MITO-002 is to be dispensed for the evening dose (RP103-MITO-002 Day 1) and to be taken every 12 hours for the remainder of participation in Study RP103-MITO-002.

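### The Day 1 checklist can be read as calling for an RP103-MITO-002 dose at the visit, while two other Protocol passages start that supply with the evening dose

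*Protocol*

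**What the plan says.** Day 1 of the extension is also the exit day of RP103-MITO-001, so the change of drug supply happens within one day. Protocol Section 10.1.1, the checklist for that visit, handles the change in a single bullet that contains three instructions in this order:

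- On the parent-study supply: "The final dose of study drug labeled for the RP103-MITO-001 should have been taken that morning"
- On the extension supply, in the sentence at issue: "Administer study drug labeled for RP103-MITO-002, with instructions to subject to take first dose of study drug for RP103-MITO-002 12 hours later than evening"
- On supply to take home: "Dispense RP103 for home administration"

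The last two words of the second instruction look like a typing slip for *that evening*.

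Two other places in the Protocol describe the same change of supply. Footnote e to the Schedule of Events says "RP103 from the previous Study RP103-MITO-001 must be taken for the morning dose and associated PK blood draws on the day of Study Exit", and continues "Then, RP103 for Study RP103-MITO-002 is to be dispensed for the evening dose (RP103-MITO-002 Day 1) and to be taken every 12 hours". Section 9.5 assigns the morning dose in the same way and adds that "study drug labeled for Study RP103-MITO-002 is to be dispensed for the evening dose". The SAP reproduces footnote e under its Table 1.

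The Schedule of Events also marks RP103 administration at Day 1. It does not say which supply or which dose is meant, and footnote e is attached to the dispensing and collection row instead.

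**The concern.** Section 10.1.1 is the list that site staff work through on the day. After recording that the morning dose has been taken, it tells them to administer the extension drug, and then has the subject take the first dose of that drug 12 hours later. Both parts cannot be true: if a dose is given at the visit, the evening dose is not the first.

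A site that acts on the verb could give a dose that the other two passages do not describe. This is an instruction on how much drug a child receives, in a trial that admits subjects from 5 kg (Section 8.1), and Section 9.5 intends the total daily dose to carry over unchanged from the parent study. The passages need to agree for that reason, whatever the effect on the analysis.

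**Working it through.** No sample-size or error-rate formula applies. The check is a comparison of passages and a count of doses.

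**Step 1: Day 1 doses under each passage**

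| Source | Morning | At the visit | Evening |
|---|---|---|---|
| Footnote e, Schedule of Events (and SAP copy) | RP103-MITO-001 supply | none described | RP103-MITO-002 supply |
| Section 9.5 | RP103-MITO-001 supply | none described | RP103-MITO-002 supply |
| Section 10.1.1, verb read literally | RP103-MITO-001 supply | RP103-MITO-002 supply | RP103-MITO-002 supply |
| Section 10.1.1, guided by its reference to the first dose | RP103-MITO-001 supply | none | RP103-MITO-002 supply |

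The third row conflicts with the first two. The fourth agrees with them, but only if the verb is set aside.

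**Step 2: size of the difference**

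Inputs: each 12-hourly dose is half of the prescribed total daily dose (Section 7.3), and the total daily dose is carried over from RP103-MITO-001 (Section 9.5). Assumption: the visit dose is one ordinary 12-hourly dose, since Section 10.1.1 gives no amount.

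- Footnote e and Section 9.5: 2 doses × 1/2 = 1.0 times the total daily dose.
- Section 10.1.1, literal: 3 doses × 1/2 = 1.5 times the total daily dose.
- Difference: one dose, 1.5 − 1.0 = 0.5 of the total daily dose.

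**Step 3: does the text settle what the verb means?**

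Not from the bullet itself. If the verb were a slip for dispensing, the bullet would order dispensing twice, because a separate sentence already does so. The quarterly and exit checklists (Sections 10.1.2 and 10.1.3) use the same verb for giving a dose at the visit, and Section 9.5 speaks of supervised administration during study visits. Against that, the sentence's own reference to the first dose points to the evening. The Day 1 mark in the Schedule of Events is compatible with either reading, because the morning and evening doses both fall on that day.

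**Step 4: effect on the SAP analyses**

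- Relative days (SAP 4.2.8) count from the day of the first dose. The first extension dose falls on the same calendar date under both readings, so they do not change.
- Exposure in days (SAP 4.6.1) is last dose minus first dose plus 1. It does not change either.
- Baseline (SAP 4.2.9) is the Day 1 value, with no reference to dose time.
- Treatment emergence (SAP 4.6.2) could change only in a corner case: an event with a missing start time or partly missing start date that stops between the visit and the evening dose.
- The compliance measure (SAP 4.6.1) counts days with a missed dose, so it cannot show an extra dose. The listing of every dosing event, from diaries and in-clinic records, could.

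**The case against.** The strongest reply is that this is a slip of wording that no careful site would follow. The sentence itself places the first extension dose 12 hours later, as do footnote e and Section 9.5, so three doses result only if that phrase is ignored. This stands to the extent that an extra dose is possible and not certain: a site *could* give it. It does not remove the contradiction, because the separate dispensing sentence leaves the meaning of the verb open.

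Several stronger readings are tempting, and the documents do not support them:

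- **That the Schedule of Events confirms a visit dose of extension drug.** It names neither supply nor dose and is compatible with footnote e.
- **That the extra dose takes children to a level known to be poorly tolerated.** A reader might apply the cystinosis figures in Section 5.2 (1.30 × 1.5 = 1.95 g/m², the stated daily maximum there). Neither document gives any subject's dose in RP103-MITO-001. The intolerance described in Section 5.2 concerns immediate-release cysteamine at that dose level, not one day's total of the delayed-release product.
- **That the visit dose would closely follow the morning dose.** Section 10.1.1 gives no interval. A morning visit is plausible from the timing of the blood samples, but this is an inference.
- **That the SAP's time anchors are undermined.** Relative days and exposure in days are identical under both readings.

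It can also be said that the point is moot, since SAP Section 1.1 reports that the study closed early. A correction can no longer protect a Day 1 visit in this study. What was actually given on Day 1 remains a question for the study report.

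**Conclusion.** The contradiction is real and is wrong as written. Section 10.1.1 conflicts with itself and with footnote e, its copy in the SAP, and Section 9.5. Followed literally, it gives three doses on Day 1, or 1.5 times the total daily dose, on the assumption that the visit dose is one ordinary 12-hourly dose. The documents do not show that any subject received a third dose.

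The point matters because it concerns an operational dosing instruction in children. The statistical consequence is minimal. This review does not say which instruction is right.

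**What to change.** Reconcile Section 10.1.1 with footnote e to the Schedule of Events, its copy in the SAP, and Section 9.5. State in one place how many doses of RP103 are taken on Day 1, from which labelled supply and at what time, and say which of these the Day 1 administration mark in the Schedule refers to. The sponsor decides which instruction governs. The cost is a short text correction and a table note, made before the wording is reused elsewhere.

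Because the study has closed, also review the Day 1 in-clinic administration records and subject diaries for a third dose, and report any found as a study drug dosing violation under SAP Section 3.2. The dosing-event listing in SAP Section 4.6.1 already draws on these records, so the cost is a check of one day per subject. The check should not rely on deviations reported by sites, since a site that followed Section 10.1.1 literally may not have regarded the dose as a deviation.
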